9.2.2 Analysis of Secondary Outcomes

The following secondary analyses will be performed:

- Proportion of subjects who tolerate 4443mg or more of egg protein in the active and control groups, following cessation of all egg intake for 6 weeks (sustained unresponsiveness), using a two-sided Fisher's exact test.
- The incidence of adverse events experienced between active and control groups. Statistical differences will be determined using two-sided Fisher's exact test for proportions; non parametric tests for graded reactions. Logistic regression will be used to assess the association of age, gender, asthma status and prior history of anaphylaxis with incidence of adverse events.
- Completion rates in the active and control groups will be compared using a two-sided Fisher's exact test.
- Change in quality of life assessments before and after OIT, as assessed by FAQL-Q in children, teenagers and their parents – between the active and control groups using two independent sample t test (or Mann-Whitney U test if normality assumption is not tenable). The changes within each group will be assessed using paired t test (or Wilcoxon signed rank test if normality assumption is not tenable).
- Immunological outcome measures pre- and post- of OIT, using paired t test (or Wilcoxon signed rank test if normality assumption is not tenable) within each group.

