2 HYPOTHESIS AND OBJECTIVES

2.1 Hypothesis

Oral immunotherapy (OIT) using pancake is safe and effective in desensitising egg-allergic children to cooked egg.

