2.3 Secondary Objectives

1. To evaluate the efficacy of pancake OIT in inducing sustained unresponsiveness in egg-allergic children.
2. To evaluate the safety and feasibility of using pancake as OIT for egg-allergic children.
3. To compare immunological outcomes (skin prick test to egg white, serum IgE to egg white, ovomucoid, ovalbumin) at baseline and end of OIT program.
4. To assess the impact of OIT on health-related quality of life.
5. To compare the immune cell profiles at baseline and end of OIT program.
6. To identify the mechanistic basis of resistance, desensitisation and SU to OIT.

2.4 Potential Risks and Benefits:

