2.4.1 Potential Risks

Allergic reactions are expected during baseline challenges to cooked egg and baked egg and they also frequently occur through the course of OIT. The risk of experiencing an allergic reaction is higher in those undergoing OIT than those who are avoiding the allergen (9). Most adverse events are expected to be mild and local reactions (itch in mouth, rashes, abdominal pain or nausea). However, systemic reactions including anaphylaxis can occur, either in the hospital during FC/ updosings or with home doses.

It has been reported that small number of patients (~2%) undergoing OIT can develop eosinophilic oesophagitis (EoE), which is almost always reversible by stopping OIT, without long-term sequelae.

Risks from venepuncture are low and mainly associated with transient discomfort which can be mitigated by the use of local anaesthetics.

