4.3.2.5 Home Instructions & Checklist

Prior to discharge post initial escalation (pancake or cookie), each family will be provided with:

- A symptom advice sheet including instructions in the prompt recognition of allergic reactions.
- A food allergy action plan. Subjects and their families will be instructed in the use of adrenaline auto-injectors, antihistamines and salbutamol (if known to be asthmatic). The expiry date of medications will be checked, and a prescription for replacements provided if needed.
- A daily dosing diary and instruction sheet which will include the following:
 - Contact information for the team, which will include a dedicated mobile phone number with 24/7 access to a member of the medical team for urgent queries, and an email address which will be checked daily by the research team from Monday to Friday for non-urgent queries.
 - Information to GP / Children's Emergency in writing that the patient is undergoing OIT and that allergic reactions may occur during administration.
 - Instructions on study dose administration including the dose to give their child and advice to avoid intense physical exercise up to 2 hours before and after the dose intake. Subjects will be asked to log all doses taken at home and any resulting adverse events. In the event of any symptoms, the family needs to contact the study team for advice and record all symptoms, duration, timing in relation to immunotherapy dose and any exacerbating factors (e.g. exercise, excessive tiredness, viral illness)
 - Dietary advice on egg avoidance (See Section 6.4).

All control subjects will receive a food allergy action plan, instructions on use of adrenaline auto-injectors, antihistamines and salbutamol if needed, as well as dietary advice on strict egg avoidance.

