Only 2 studies have evaluated using baked egg in OIT and both used different doses administered over different durations of time. In the study by Bravin et al, biscuits containing varying amounts of egg protein were administered to baked egg allergic subjects, starting at 125µg and increased daily over 60 days to a target maximum dose of 6.25g after which an open FC to 1 boiled egg was performed to assess for desensitisation. Of the 15 patients recruited, 12 (80%) completed the OIT program and all adverse reactions were mild. The second study by Bird et al. did not report the starting OIT dose but baked egg-allergic subjects underwent an initial escalation phase up to 125mg in hospital followed by home up-dosing to a maintenance dose of 3.8g which was continued for 1 year. This was followed by an open FC to 6g of lightly cooked egg to assess for desensitisation. Again, dosing was well tolerated with only 77 adverse reactions reported of 5605 total recorded doses (1.37% of total doses) and none requiring adrenaline.

Pancakes are expected to be less allergenic than cooked egg because of the wheat matrix but more allergenic than baked egg. In our study, all subjects assessed to be baked egg tolerant will have ingested and tolerated 2.5g of egg protein during the baseline baked egg open FC. BET subjects will hence commence pancake OIT at 37.5mg (1.5% of the 2.5g cumulative dose tolerated during the baked egg FC) with increments every 30minutes to a maximum of 300mg during the initial escalation phase (Table 4). The starting dose of the build-up phase will be 1 step below the dose tolerated during the initial escalation phase to minimise risk of allergic reactions at home, particularly as the presence of co-factors may decrease reaction threshold (see Section 6.4). Dose increments during the build-up phase will occur every 4 weeks (minimum 3 weeks) until a target maintenance dose of 2500mg is achieved (Table 5). Subjects will then remain on the daily maintenance dose for a minimum of 16 weeks or total OIT duration of 18 months, whichever is achieved earlier.

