9.2 Statistical and Analytical Plans

The primary analysis will be performed on an intention to treat basis: all subjects allocated to each arm will be analysed together as representing that treatment arm, irrespective of compliance and whether or not they have completed the prescribed regimen. A secondary

analysis will also be performed on a per protocol basis. Statistical analysis was performed using SAS software version 9.4 for Windows (Cary, NC: SAS Institute Inc.). Statistical significant is set at $p < 0.05$.

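### Section 2.1 hypothesises that pancake OIT is safe, but the difference tests in 9.2.2 cannot support that claim, and they have little power for uncommon severe reactions

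*Combined protocol and SAP*

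**What the plan says.** Section 2.1 states a single hypothesis: "Oral immunotherapy (OIT) using pancake is safe and effective in desensitising egg-allergic children to cooked egg". Section 2.3 makes safety a secondary objective: "To evaluate the safety and feasibility of using pancake as OIT for egg-allergic children". Neither section, nor any other, gives an acceptable rate, a margin or a confidence-interval rule for concluding that the product is safe.

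Section 9.2.2 lists "The incidence of adverse events experienced between active and control groups" as a secondary analysis and continues: "Statistical differences will be determined using two-sided Fisher's exact test for proportions; non parametric tests for graded reactions". The same bullet adds a logistic regression of adverse events on age, gender, asthma and prior anaphylaxis. Section 9.2 sets the threshold ("Statistical significant is set at" p < 0.05). No interval estimate and no per-dose rate is planned for adverse events.

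Four other places bear on this:
- Section 2.4.1: "The risk of experiencing an allergic reaction is higher in those undergoing OIT than those who are avoiding the allergen".
- Section 7.2 makes every anaphylaxis in response to an OIT dose an adverse event of interest. Section 9.2.2 does not mention anaphylaxis as an outcome.
- Section 4.3.2.5: "Subjects will be asked to log all doses taken at home and any resulting adverse events".
- Section 6.1, on an earlier baked-egg study: "dosing was well tolerated with only 77 adverse reactions reported of 5605 total recorded doses (1.37% of total doses").

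**The concern.** A test of no difference answers a different question from the one in 2.1. For reactions of any kind, the protocol itself expects the null to be false, so a significant result confirms what was already expected and does not say whether the excess is acceptable. For uncommon severe reactions, a non-significant result is likely even with a large true excess. Neither result leads to a conclusion that the product is safe.

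Section 1.2.1 says that no study of pancakes in egg OIT has been published, so this trial's safety statement may be the first that readers see. It should show how large a risk the data leave open. The planned p-values do not show that, although the diaries that would allow a better answer are already part of the trial.

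**Working it through.** **Inputs from the documents.** 22 active and 11 control children (3.1, 9.1); two-sided Fisher (9.2.2); p < 0.05 (9.2); 30% attrition (9.1); 77 reactions in 5,605 doses (6.1); OIT lasting at least 12 months (4.3.2.6). The documents give no expected anaphylaxis rate, so every severe-event count or rate below is an assumption.

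**The plan's own figures.**
- 77/5605 = 1.37%, as stated.
- The sample size is built on desensitisation only. With 65% v 15% at 2:1 and unpooled variance, controls = (1.960 + 0.842)² × (0.15×0.85 + 0.65×0.35/2) / 0.50² = 7.57. The total is 3 × 7.57 = 22.7, rounded up to 23, and 23/0.70 = 32.9, rounded up to 33. The stated 33 reproduces, but nothing in it concerns safety.

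**How many events Fisher needs.** Take 7 events in 33 children, all in the active arm. The hypergeometric probability of the observed table is C(22,7)/C(33,7) = 170,544/4,272,048 = 0.0399. The tables at least as unlikely have 0, 1 or 2 active events, with probabilities 0.0001, 0.0024 and 0.0250. The two-sided p is 0.0399 + 0.0001 + 0.0024 + 0.0250 = 0.067.

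| Active | Control | Two-sided p |
|---|---|---|
| 7/22 | 0/11 | 0.067 |
| 8/22 | 0/11 | 0.031 |
| 10/22 | 1/11 | 0.054 |
| 11/22 | 1/11 | 0.027 |
| 7/15 | 0/8 | 0.052 |

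With no control events, significance needs 8/22 = 36% of treated children. With one control event it needs 11/22 = 50%. The last row approximates 30% attrition (22 × 0.7 = 15.4; 11 × 0.7 = 7.7).

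**Exact power at 22 v 11.** Power is the sum, over all tables with p < 0.05, of the product of the two binomial probabilities.

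| Assumed active rate | Power v 5% control | Power v 0% control |
|---|---|---|
| 20% | 3% | 6% |
| 30% | 20% | 33% |
| 40% | 48% | 71% |

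**What estimation would show.**
- 7/22 = 31.8%, exact 95% CI 13.9% to 54.9%. The Newcombe 95% CI for the difference from 0/11 is 1.7 to 52.7 percentage points.
- 0/22 has an exact two-sided upper limit of 1 − 0.025^(1/22) = 15.4%, so even no events at all would leave a sizeable risk open.

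**Per-dose information.** If 15 to 22 children each take a daily dose for 365 days, the diaries hold 15 × 365 = 5,475 to 22 × 365 = 8,030 doses. That is enough to estimate a per-dose rate. Reactions cluster within children, so the interval must be wider than one that treats doses as independent.

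**The case against.** The tempting stronger reading is that the trial will take a non-significant Fisher result as proof of safety. The documents do not support that. Section 9.2.2 speaks only of determining statistical differences, 2.3 of evaluating safety, and 2.4.1 and 2.4.2 openly acknowledge more frequent reactions on OIT. The plan does not rule the reading out, but it does not state it either.

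Four further points stand:
- **No between-arm test of anaphylaxis is named.** Section 7.2 ties the event of interest to an OIT dose, which a control child does not take. The 7/22 v 0/11 table is an illustration.
- **Fisher is not weak for everything.** At an assumed 80% v 20% for any reaction, exact power at 22 v 11 is 89%. As an example, 22/22 v 8/11 gives p = 0.030.
- **Safety does not rest on Fisher alone.** Graded comparisons are also planned. If seven active children had grade 3 and everyone else grade 0, an asymptotic Mann-Whitney test gives p = 0.041 and a permutation version about 0.068. Other assumed grade mixes gave asymptotic p-values from about 0.0003 to 0.09. These are still difference tests with no safety criterion, and the plan does not say whether the unit is the child or the reaction.
- **The 1.37% is not a benchmark.** Section 6.1 gives it as background from a study of baked egg in baked-egg-allergic children. The same section expects pancake to be more allergenic than baked egg, and this trial also enrols baked-egg-tolerant children.

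Safety is also a secondary objective. The primary analysis, eligibility and data capture do not depend on this point.

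**Conclusion.** The point holds in limited form. The claim in 2.1 has no criterion, and the planned difference tests cannot supply one whichever way they come out. The practical weakness is confined to uncommon severe reactions. At 22 v 11, about 36% of treated children would have to be affected against none in control before Fisher reached p < 0.05, and power is 3% at 20% v 5% and 20% at 30% v 5%. These figures assume that all 33 children are analysed and that the illustrative rates apply. The argument that a difference test cannot establish safety needs neither assumption.

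This should be fixed, but it does not threaten the trial's primary result.

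**What to change.** In 9.2.2, make estimation the main safety analysis:

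1. Report the number of children with anaphylaxis or an adrenaline-treated allergic reaction, by arm, with exact 95% CIs and the risk difference with its CI. Count events from any cause in both arms, because an event tied to an OIT dose cannot arise in a control.
2. Report dosing reactions per 100 doses in the active arm from the diaries, with a CI that allows for clustering within child (for example, a bootstrap that resamples children). Cite the 1.37% only as context, and say that product and population differ.
3. Base graded comparisons on the worst grade per child, so that each child counts once.
4. State that a non-significant test will not be taken as evidence of safety. In 2.1, replace the claim of safety with an aim to estimate the safety profile.

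The Fisher tests can stay as supporting results.

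Cost: no extra children, visits or data, and a little more analysis. The safety claim becomes more modest. Changing 2.1 and 9.2.2 is a protocol amendment, which section 12 requires to be notified to the CIRB.

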- There is insufficient or incomplete evidence to make a clinical judgement of the causal relationship.

7.3 Collecting, Recording and Reporting of Adverse Events and Serious Adverse Events to CIRB

All adverse events will be recorded on a subject's diary from the time the participant provides consent until the time the event resolves or until 30 days after the participant completes study treatment. Adverse events may be discovered through observing and questioning the participant or receiving an unsolicited complaint and questioning the participant in an objective manner. All adverse events will be recorded, regardless of their severity or relation to study medication or procedures.

Reporting of adverse events involves the PI submitting to the approving CIRB the completed SAE Reporting Form within the stipulated timeframe. PI is responsible for informing the institution representative (local SAE resulting in death), sponsor or regulatory bodies as required and appropriate.

Reporting timeline to CIRB:

- SAE that result in death, regardless of causality, should be reported immediately - within 24 hours of the PI becoming aware of the event.
- All "related" SAE (definitely / probably / possibly) irrespective of severity or expectedness, need to be reported to CIRB within 24 hours of the PI becoming aware of the event.

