9 SAMPLE SIZE AND STATISTICAL METHODS

9.1 Determination of Sample Size

The incidence of natural resolution of egg allergy over 12 month period is about 15% (4),(10). The efficacy for desensitisation using raw/cooked eggs is about 80% (ranging between 55% -100%) whilst that for OIT using baked egg products is about 50%. As there are no prior studies using pancake to desensitise egg-allergic patients, we are estimating the efficacy to be in between that of raw/cooked eggs and baked eggs, at about 65%. We plan to recruit 33 egg-allergic children to the study, who will be randomised 2:1 to active (n=22) or control (n=11) groups. This will allow us to detect a difference in rates of desensitisation of 50%, with 80% power using a two-sided significance level of 0.05, whilst allowing for a 30% attrition rate. Sample size calculation was performed using PASS 14 (Power Analysis and Sample Size Software (2015). NCSS, LLC. Kaysville, Utah, USA, [ncss.com/software/pass.](http://ncss.com/software/pass/)).

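### Section 9.2.2 compares adverse event occurrence between arms only as any/none per child, ignoring event counts and unequal time at risk

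*Combined protocol and SAP*

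**What the plan says.** Section 9.2.2 lists, as a secondary analysis, "The incidence of adverse events experienced between active and control groups. Statistical differences will be determined using two-sided Fisher's exact test for proportions". It adds unspecified non-parametric tests for graded reactions, and a model for predictors: "Logistic regression will be used to assess the association of age, gender, asthma status and prior history of anaphylaxis with incidence of adverse events". That model is binary, has no exposure term and does not list treatment arm. Nothing in section 9.2 mentions an event count, a rate, an offset for follow-up, or a rule for children followed for different lengths of time.

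Other sections bear on this:

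- **Time at risk.** Section 4 sets total OIT duration at 12 to 18 months. Section 4.3.2.6 places the control children's exit challenge between 12 and 18 months. Section 9.1 allows for 30% attrition.
- **What is recorded.** Section 7.3 puts adverse events on a subject's diary from consent and states: "All adverse events will be recorded, regardless of their severity or relation to study medication or procedures".
- **Home diary.** Section 4.3.2.5, listing what families receive after initial escalation, says: "Subjects will be asked to log all doses taken at home and any resulting adverse events". The control package in the same section lists no diary.
- **How the plan frames safety.** Section 1.2.2 sets the safety of OIT against the risk of accidental reactions in controls. Section 2.4.2 accepts that reactions become more frequent during OIT. Section 6.1 summarises an earlier baked egg study per dose: "only 77 adverse reactions reported of 5605 total recorded doses (1.37% of total doses").

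**The concern.** The safety contrast is about frequency, but the planned test sees only whether a child ever had an event. A child with one accidental rash in 18 months scores the same as a child with ten dosing reactions. A child who stops OIT after two months because of reactions scores the same as one who reacted once in 18 months.

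Over a year or more, many children in both arms may have at least one event, the more so because section 7.3 records events of any severity and cause. The two proportions then both approach 100%, and the test cannot separate the arms however different the counts are. A severalfold excess of reactions under OIT could be reported as not significant. Safety is half of the hypothesis in section 2.1, so that result could be misread as reassurance.

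**Working it through.** **The plan's own figure.** Section 9.1 sizes the trial for desensitisation, 65% v 15%, "with 80% power using a two-sided significance level of 0.05, whilst allowing for a 30% attrition rate". An unpooled z-test gives n(control) = (1.96 + 0.8416)² × [0.15×0.85 + 0.65×0.35/2] / 0.5² = 7.57. The total is 3 × 7.57 = 22.7, rounded up to 23, and 23/0.70 = 32.9, so 33. The stated 33 (22 + 11) reproduces. No power is given for the adverse event comparison.

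**Inputs for the check.**
- Sample: 22 v 11, two-sided 0.05 (section 9.1).
- Active rate: 77/5605 = 1.37% of doses (section 6.1). At one dose a day, 0.0137 × 365 = 5.0 reactions in 12 months and 0.0137 × 547 = 7.5 in 18 months.
- Assumed, because the documents do not give them: the control mean m and the between-child shape k (smaller k means more spread). Counts are gamma-Poisson, so P(any event) = 1 − (k/(k+m))^k.

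Example, k=1: active 1 − 1/6 = 83%; control with mean 1, 1 − 1/2 = 50%.

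**Power with equal follow-up.** Fisher is by exact enumeration; the rank test (Mann-Whitney on counts) is by simulation.

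| Mean events, active v control | k | Any event, active / control | Fisher | Rank test | Loss (points) |
|---|---|---|---|---|---|
| 5 v 0.2 | 1 | 83% / 17% | 96% | 100% | 4 |
| 5 v 0.5 | 1 | 83% / 33% | 77% | 98% | 21 |
| 5 v 1 | 1 | 83% / 50% | 46% | 84% | 38 |
| 7.5 v 1 | 1 | 88% / 50% | 62% | 96% | 34 |
| 5 v 0.5 | 0.5 | 70% / 29% | 49% | 81% | 32 |
| 5 v 1 | 0.5 | 70% / 42% | 24% | 53% | 29 |
| 5 v 2 | 2 | 92% / 75% | 21% | 66% | 45 |
| 7.5 v 2 | 2 | 96% / 75% | 33% | 95% | 62 |
| 1 v 1 (no difference) | 1 | 50% / 50% | 2.7% | 4.5% | – |

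At 5 v 1, k=1, simulating Fisher as well gives about 44%, hence the range 44-46%. The last row shows that the rank test does not gain power through excess false positives.

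**Power with unequal follow-up.** Here follow-up is uniform over 12-18 months, 30% of children leave early, the active rate is 5.0 per child-year, and k=1. Tests are Fisher / rank test on rates / negative binomial with log follow-up offset:
- control 0.25 per year: 90 / 100 / 100%
- control 0.5: 68 / 96 / 100%
- control 1: 41 / 81 / 93%
- control 2: 14 / 40 / 57%
- control 3: 7 / 14 / 20%

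The loss shrinks at both ends: when few controls have an event Fisher is already strong, and when the rates are close no test has much power. With k from 0.5 to 2, the loss against the rank test runs from 1 to 52 points. Under no difference, rejection is about 1-4% for Fisher, close to 5% for the rank test and about 5-8% for the negative binomial.

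**A check that needs no rate.** If all 22 active children have an event, Fisher gives p=0.030 with 8 of 11 controls affected and p=0.104 with 9 of 11. At least 3 controls must be entirely event-free for significance.

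**Sensitivity to unequal reporting.** Suppose true rates are equal but controls report half their events (an assumption). False positives, Fisher v rank test on counts, are about 10% v 15% at mean 1, k=1; 15% v 31% at mean 2, k=2; and 16% v 36% at mean 3, k=2.

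**The case against.** The strongest objection concerns the data. A reader might infer that every child already has a dated event count from a daily diary, so that only the test need change. The documents do not show that. The dosing diary in section 4.3.2.5 goes to families after initial escalation, so to the active arm. Section 7.3 speaks of a subject's diary but sets no schedule for controls. Section 4.3 gives controls 2 hospital visits against 9 to 11 for active children. If controls under-report, both analyses are biased and the rate analysis more so, as shown above. This stands, and equal capture has to be part of the change.

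Second, only active children undergo the baked egg challenge, the initial escalation and the hospital updosing. A plain count from randomisation would include reactions that controls cannot have. This also stands and shapes the fix.

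Third, this is a secondary outcome, section 2.4.1 already expects more reactions with OIT, and a non-significant result would not establish safety. The grading tests and the completion-rate comparison carry some further safety information. This limits the consequence. It does not supply a count or a time at risk.

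Fourth, the rate anchor comes from baked egg OIT, and section 6.1 expects pancake to be more allergenic than baked egg. The anchor is therefore only indicative.

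**Conclusion.** The point holds as a weakness in the choice of analysis. The between-arm test of occurrence reduces each child to any/none and uses neither the number of events nor time at risk, while the plan's question is about frequency. The cost in power ranges from a few points when few controls have any event to about 40-60 points when most children in both arms have one.

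That range rests on an assumed control rate, an assumed spread between children, gamma-Poisson counts and an active rate borrowed from another product. Three stronger readings are tempting and not supported:

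- **A loss of about 40 points as a ceiling or a property of this trial.** It is one scenario among many, and 62 points occurs within the same assumptions.
- **A contradiction of the stated 80% power.** That figure belongs to the desensitisation outcome only.
- **No other safety analysis is planned.** Graded reactions are tested, though without counts or follow-up.

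The change should be made, but it does not threaten the primary analysis.

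**What to change.** In section 9.2.2:

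1. Make the main between-arm comparison the rate of allergic reactions per child-month, from randomisation to T3 or last contact. Exclude reactions at scheduled food challenges. Count reactions at in-hospital escalation and updosing separately, because only active children have these visits.
2. Test it with a Mann-Whitney U or permutation test on each child's rate.
3. Report a rate ratio with 95% CI from a negative binomial model with log follow-up time as offset, where it converges.
4. Keep the number and percentage of children with at least one event, with Fisher's test if wanted, as a supporting line.

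In sections 7.3 and 4.3.2.5, state that the adverse event diary applies to control children in the same way as to active children.

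The cost is SAP wording, a little more analysis, a follow-up time for each child, and a diary for 11 control families if none is now issued. Remaining weaknesses are sensitivity to unequal reporting and a negative binomial model that can be slightly liberal or unstable at 33 children. The second is why the rank or permutation test should be the main test.

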1.2.3 Rationale for Study Population

Egg allergy is one of the commonest food allergies affecting children. Most published egg OIT trials include patients above 4-5 years of age as these patients are believed to have a lower chance of acquiring natural tolerance without intervention. Given that OIT may potentially accelerate tolerance acquisition in younger children, we have chosen to include subjects between 2-15 years old in this study. Furthermore, recruiting children of a wider age range will allow us to better assess the safety and feasibility of using pancakes for OIT in children of various ages, particularly the acceptability of pancake in the younger cohort.

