4.3 Study Visits and Procedures Overview

There will be 9-10 hospital visits for the BET group, 10-11 hospital visits for the BER group over the entire study duration. There will be 2 hospital visits for the control group.

[figure not shown]

Figure 2: POET Study Timeline

Study Timepoints	TS	T0	T1C		T1P/ T2P		T3	T4
	Screening & Cooked Egg FC	Baked Egg FC	Cookie Initial Escalation	Home Cookie Build-up	Pancake Initial Escalation	Hospital Pancake Build-up	Exit Cooked Egg FC	SU FC
Informed consent	X							
Medical history	X							
Concomitant medications	X	X	X		X	X	X	X
Adverse events		X	X	X	X	X	X	X
Physical exam	X	X	X		X	X	X	X
Spirometry		(X)					(X)	
Asthma control test	X	(X)					(X)	
SCORAD	X							
POEM	X							
Skin Prick Test	X*						X	X
Blood test	X*						X	X
HRQL Assessments	X		X		X		X	X

Table 1: Study Procedures

(X) may be performed, depending on clinical need; X* - Results from SPT/ IgE performed within 3 months prior will be used and need not be repeated

X are procedures applicable to control subjects

FC – Food Challenge; SU – Sustained Unresponsiveness

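### Feasibility of pancake OIT is an objective, but the only planned analysis of completion is an insensitive comparison with controls, with completion left undefined

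*Combined protocol and SAP*

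**What the plan says.** Section 2.3 lists as its second objective "To evaluate the safety and feasibility of using pancake as OIT for egg-allergic children". Feasibility also appears in the study aim (section 1.2) and the design statement (section 4). Section 1.2.3 defends the wide age range partly on feasibility, "particularly the acceptability of pancake in the younger cohort". Section 1.2.1 argues for pancakes from poor adherence to baked egg products and cites a baked egg OIT study with 38% withdrawal.

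Section 9.2.2 labels no analysis as feasibility. The one item that concerns completion reads: "Completion rates in the active and control groups will be compared using a two-sided Fisher's exact test". It gives no definition of completion, no interval and no criterion. No analysis of doses taken, of reaching the maintenance dose or of acceptability by age is listed.

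On the burden in each arm, section 4.3 says "There will be 2 hospital visits for the control group", against 9 to 10 visits for baked egg tolerant and 10 to 11 for baked egg reactive children on OIT. Section 4.3.3 makes T3 the final visit for controls. Section 4 sets OIT duration at 12 to 18 months, with daily home doses.

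**The concern.** Feasibility here is a question about one treatment: can families prepare and give pancakes daily, climb to Step 7 and stay there? A between-arm test of completion answers a different question, because the event is not the same in the two arms. A control completes by returning once after screening while continuing standard care. An active child completes by sustaining a demanding home regimen and many supervised visits. A significant difference would show mainly that avoidance is easier to see through. A non-significant one, with 11 controls, would say little about pancakes.

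Leaving completion undefined adds a second problem. Attending T3, reaching Step 7 and finishing maintenance can give three different rates in the same 22 children. Unless one is fixed beforehand, the choice can be made after the data are seen. At stake is whether the trial can report a clear, pre-specified feasibility result for a product it calls novel.

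**Working it through.** **Inputs.** Arm sizes come from section 9.1, "who will be randomised 2:1 to active (n=22) or control (n=11) groups". The significance level is two-sided 0.05 (sections 9.1 and 9.2). The 38% withdrawal is from section 1.2.1. The documents give no expected control completion rate, so control non-completion of 0%, 5% and 10% is assumed.

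**The plan's own figure.** No power is stated for completion. The only sample size figure is 33, for the primary outcome at 65% versus 15%, "with 80% power using a two-sided significance level of 0.05, whilst allowing for a 30% attrition rate". It reproduces with the unpooled normal approximation:

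- controls = (1.960 + 0.842)² × (0.15 × 0.85 + 0.65 × 0.35 / 2) / 0.50² = 7.57
- 7.57 / 0.7 = 10.8, so 11 controls
- 2 × 7.57 / 0.7 = 21.6, so 22 active

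The trial was therefore sized for a 50-point difference in desensitisation, not for completion.

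**Fisher's exact test, two-sided, 22 versus 11.** For 7 non-completers, all in the active arm, the hypergeometric terms no larger than the observed one (0.0399) are 0.0399 + 0.0250 + 0.0024 + 0.0001 = 0.067.

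| Active not completing | Control 0/11 | Control 1/11 | Control 2/11 |
|---|---|---|---|
| 6/22 (27%) | 0.077 | 0.378 | 0.687 |
| 7/22 (32%) | 0.067 | 0.218 | 0.681 |
| 8/22 (36%) | 0.031 | 0.212 | 0.430 |
| 10/22 (45%) | 0.013 | 0.054 | 0.249 |
| 11/22 (50%) | 0.005 | 0.027 | 0.132 |
| 13/22 (59%) | 0.002 | 0.009 | 0.034 |

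With every control completing, significance begins at 8/22. One lost control moves it to 11/22, and two move it to 13/22.

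**Exact power.** This sums the two binomial probabilities over all tables with p < 0.05. With no control failures it reduces to P(X ≥ 8) for X ~ Binomial(22, 0.32) = 0.41.

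| True active non-completion | Control 0% | Control 5% | Control 10% |
|---|---|---|---|
| 30% (the attrition allowance in section 9.1) | 33% | 20% | 12% |
| 32% | 41% | 25% | 15% |
| 38% (cited withdrawal) | 64% | 42% | 28% |

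**Active arm alone.** For 15/22 completing, the Clopper-Pearson limits are the 2.5% point of Beta(15, 8) and the 97.5% point of Beta(16, 7). Completion is 68.2%, 95% CI 45.1% to 86.1%, so non-completion is 31.8%, CI 13.9% to 54.9%. That interval contains 38%. The upper limit for non-completion falls below 38% only with 19 or more completing (3/22: upper limit 34.9%; 4/22: 40.3%).

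**The case against.** The best defence is that section 9.2.2 never calls this item the feasibility test. It can be read as a check on differential attrition, for which a between-arm comparison is reasonable. That stands, and it limits the point: the gap is a missing feasibility analysis and an undefined term, not an invalid test. On this reading, however, adherence and completion of OIT have no planned analysis of their own.

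Two stronger readings are tempting. A reader might infer that a non-significant result will be taken to show feasibility; the documents contain no such decision rule. A reader might also infer that the test would miss a 32% failure rate. That is true only in the sense that an observed 7/22 against 0/11 is not significant. A true rate of 32% would still be detected about 41% of the time if no control failed, and comparing the rates requires computing the active one, so it would be visible whatever the p value.

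Other items in section 9.2.2, such as adverse events with age as a covariate and change in quality of life, bear on tolerability and burden. They do not measure adherence or reaching maintenance.

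Finally, the alternative is not decisive either. With 22 children the interval is wide. The 38% comes from baked egg allergic children on a different product, whereas this active arm includes baked egg tolerant children. Setting the two side by side is description only.

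**Conclusion.** The concern holds as a gap in the secondary analysis plan. The plan fixes no meaning for completion and provides no active-arm estimate with an interval. Its one relevant comparison sets 12 to 18 months of daily OIT against, in effect, a single return visit. At 22 versus 11, 32% observed non-completion is not significant even with perfect control completion, and power for a true 32% is about 15% to 41% over the assumed control rates.

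Two inferences support this: that the completion item is the nearest the plan comes to a feasibility analysis, and that control completion means attending T3, read from the visit schedule because no definition is given. Both follow from the documents but are not stated there. The primary analysis is not affected. The change is worth making because it is cheap and gives a stated objective a usable answer.

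**What to change.** In section 9.2.2, replace the completion item with a feasibility analysis of the active arm:

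- Define completion before analysis. State how a child who reaches the 18-month limit before 16 weeks at Step 7 is counted.
- With all children randomised to active as the denominator, report the proportion reaching Step 7 and the proportion completing the planned maintenance, each with an exact 95% CI.
- Summarise descriptively the percentage of prescribed doses taken, from the home diary (section 4.3.2.5), and weeks to Step 7 among those who reach it, beside the number who do not.
- Show these overall and, descriptively, by age under 5 versus 5 and over, already a minimisation factor (section 4.1).
- Keep T3 attendance by arm only as a check on differential missing outcome data.
- If a feasibility threshold is wanted, set it in advance.

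The cost is mainly wording. Step 7 dates come from the supervised updosing visits and doses from the diary. Reasons for stopping would be useful, but the documents do not show that they are recorded: section 4.4.2 lists only skin prick test, blood tests and quality of life at an optional visit. They would need one added field on the data form. Sample size, visits and treatment do not change. The estimates will be imprecise at n = 22, and more so by age.
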